Hydroxychloroquine and Cognitive Function after Surgery

NCT03025087

[figure not shown]
Document Date: 11/29/2020

Hydroxychloroquine and Cognitive Function after Surgery

Purpose of the study

As our population ages, the manifestations of systemic atherosclerosis (stroke, cognitive impairment) extend the burden on the healthcare delivery system. The consequences of atherosclerosis are particularly relevant during surgery, where perioperative neurologic events can have a dramatically detrimental effect on the duration and quality of survival. The long-term objective of our multidisciplinary Neurological Outcome Research Group (NORG) is to understand the mechanisms underlying neurologic and neurocognitive dysfunction after surgery and to reduce the incidence of these devastating outcomes.

This study is a pilot investigation intended to gather preliminary information to assess the efficacy of hydroxychloroquine to preserve blood brain barrier integrity, decrease inflammation, and improve cognitive function after surgery including cardiac surgery with cardiopulmonary bypass (CPB). Our study is based on a model (see Figure) that surgical trauma (irrespective of type of surgery) with general anesthesia evokes a systemic inflammatory response.(1) Damage-associated molecular pattern (DAMPs), including HMGB1, are released in the systemic circulation contributing to the permeability of the blood–brain barrier (BBB). Opening of the BBB allows peripheral cytokines and alarmins to enter the brain and the CNS, causing neuroinflammation. In the hippocampus, HMGB1 activates receptor for advanced glycation end products (RAGE) signaling thus perpetuating the inflammatory response and further contributing to neuroinflammation, including de novo synthesis of cytokines like TNF- α and IL-1 β . Activation of this positive feedback loop accounts for memory dysfunction and possibly localized synaptic/neuronal deficits.

Preliminary data from our pilot study (Pro00045387) indicates that blood brain barrier disruption occurs in about 60% of cardiac surgery patients and 50% of noncardiac surgery patients. Including an expanded cohort of patients will allow the investigation of differences in the outcomes of interest by surgery type.

The primary purposes of this pilot investigation are to:

1. Obtain data on the pharmacokinetics of hydroxychloroquine during surgery.
2. Determine the effect of hydroxychloroquine upon blood brain barrier (BBB) integrity after surgery.

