3. Determine the effect of hydroxychloroquine upon perioperative inflammation.
4. Determine the relationship between hydroxychloroquine, inflammation, BBB disruption and neurological/neurocognitive function after surgery.

Background & Significance

Cognitive decline after surgery has generated great scientific and public interest because brain dysfunction leads to a reduction in quality of life for both the patient and their family. While there has been substantial advancement in perioperative organ protection leading to reductions in mortality associated with surgery, the incidence of cognitive dysfunction has changed little over the last ten years, despite substantial advances in pharmacology and technology. This phenomenon is related in part to the changing surgical population. Although older patients are now able to safely undergo surgical procedures without serious concern over loss of life, these elderly individuals are at a substantially increased risk for central nervous system dysfunction, particularly, cognitive decline. The clinical and financial implications resulting from these problems can be profound, with prolonged hospitalization and increased resource utilization being associated with major and minor neurobehavioral deficits.

Our investigations to date demonstrate that cognitive impairment occurs frequently in the large number of increasingly elderly patients undergoing cardiac operations every year. Post-operative cognitive deficit (POCD) is present in 36% of patients at 6 weeks after surgery and importantly, persists in 42% of patients up to five years after surgery.(2) Similarly after noncardiac surgery, the incidence of POCD was over 50% at 6 weeks after surgery and approximately 45% at 1 year after surgery.(3) Moreover, perioperative cognitive decline predicts long-term cognitive dysfunction, with dysfunction resulting in reduced quality of life.(4,5)

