In animal models, the aminoquinolines have been shown to be protective against BBB dysfunction. In one study, mice were pretreated with either chloroquine or saline for six consecutive days and then given a dose of kainic acid, which is known to induce seizures and cause BBB dysfunction.(30) Animals treated with chloroquine had less IgG and serum protein extravasation into the brain compared with controls, indicating better preservation of the BBB.

In a recently completed study at Duke (unpublished data), adult male Sprague-Dawley rats underwent 60 minutes of deep hypothermic circulatory arrest (DHCA) at 18°C after being pretreated with either Chloroquine (25mg/kg) vs. PBS vehicle, or a selective quinone reductase 2 (QR2) inhibitor (25mg/kg) vs. 50% DMSO vehicle administered intraperitoneally 2 hours before CPB (n=3-4). Brain magnetic resonance imaging (MRI) was performed on postoperative day (POD) 1 using a 7T Bruker Biospec horizontal bore scanner, and neurologic function scores were assessed on POD 1 and 2. Brain samples harvested 48 hours after CPB/DHCA were used to quantify necrotic neurons (acid fuchsin-celesteine blue) in 5 representative areas of cortex and CA1 hippocampus. MRI analysis revealed a decrease in blood brain barrier permeability as measured by gadolinium chelate in animals treated with chloroquine or selective QR2 inhibitor compared to their respective control groups ($p < 0.05$). Histologically, animals treated with chloroquine or QR2 inhibitor exhibited lower numbers of cortical and hippocampal necrotic cells compared to vehicle-treated animals ($p < 0.05$, respectively). QR2 inhibition also improved neurologic function on POD1 (neurologic score 2.33 ± 0.58 in QR2 inhibitor vs 4.33 ± 0.58 in DMSO vehicle; $p < 0.05$).

As a consequence of its anti-inflammatory, antimicrobial, and BBB preservation properties and its long history of safety, particularly with short-term use, HCQ may be an ideal candidate for evaluation as a neuroprotective agent following surgery.

Design & Procedures

This study is a pilot investigation intended to gather preliminary information to assess the efficacy of hydroxychloroquine to preserve blood brain barrier integrity and improve cognitive function after surgery. In this clinical trial, up to 50 informed and consenting patients ≥ 50 years of age will be prospectively enrolled over a 1-year period to provide 30 evaluable subjects.

Study Procedure

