Patients selected for enrollment will be informed of the study, as well as the risks and benefits of participation. Patients will be invited to participate and a log of all patients and those that accept and reject the invitation will be kept. As part of enrollment, a Mini Mental Status Exam (MMSE) will be performed and all patients scoring < 26 will be excluded to minimize the possibility of early dementia in our patient samples. Similarly patients scoring ≥ 27 on the Center for Epidemiological Studies – Depression (CES-D) scale (indicating severe depression) will be excluded. If patients develop renal failure (GFR < 30 ml/min/1.73 sq.m) postoperatively (after consent), they will not receive gadolinium based contrast for MRI.

Hydroxychloroquine Administration

The average adult dose of HCQ in the initial management of lupus is 400 mg once or twice daily. Similarly, the initial dose in rheumatoid arthritis is 400-600 mg daily.(31) Recently, HCQ has been administered safely to 19 subjects at a dose of 1000 mg daily as an adjuvant to lung cancer chemotherapy (median follow-up 9.1 months).(32) We therefore propose a dose escalation protocol as follows:

- Phase 1 – 6 evaluable subjects (3 cardiac, 3 noncardiac): 1000 mg HCQ on the day prior to surgery.
- Phase 2 – 6 evaluable subjects (3 cardiac, 3 noncardiac): 1000 mg HCQ on the day prior to surgery followed by 400 mg daily until the day of MRI imaging on postoperative day 1-5.
- Phase 3 – 6 evaluable subjects (3 cardiac, 3 noncardiac): 1000 mg HCQ on the day prior to surgery followed by 400 mg twice daily (800 mg total) until the day of MRI imaging on postoperative day 1-5.
- Phase 4 – 6 evaluable subjects (3 cardiac, 3 noncardiac): 1000 mg HCQ on the day prior to surgery followed by 500 mg twice daily (1000 mg total) until the day of MRI imaging on postoperative day 1-5.
- Phase 5 – 6 evaluable subjects (3 cardiac, 3 noncardiac): 1000 mg HCQ 1-2 hours after separation from CPB or at end of noncardiac surgery followed by the highest tolerated dose from the previous 4 phases divided into 2 equal daily doses until the day of MRI imaging on postoperative day 1-5.

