A board-certified neuroradiologist, blinded to the clinical and surgical variables, will read the MRI, and also review the precontrast and postcontrast FLAIR images for the presence of HARM (hyperintense acute reperfusion marker) and classify it by location (sulcal, ventricular, and/or generalized) and severity (mild, moderate, or severe), according to the classification scheme described by Merino et al.(9)

Quantitative DCE MRI of BBB disruption

Using T1 time series data, we will calculate the rate at which the contrast agent passes from the vascular compartment into the tissue compartment, K_i , using the Patlak formulation of tracer leakage.(33) Plasma levels of gadolinium will be sampled from a region-of-interest in the sagittal sinus. Parenchymal region-of-interest measurements will be made in the white matter.

Quality of Life Assessment

Quality of life will be measured in conjunction with each cognitive assessment at baseline, 6-weeks (\pm 2 weeks),, and 1-year (\pm 1 month) in all enrolled patients. We will use an instrument that includes a measure of functional status derived for use in cardiovascular populations (the Duke Activity Status Index or DASI), psychological measures including depression (the CES-D), the State Trait Anxiety Inventory (STAI), the Hopkins Symptom Checklist (SCL-90), social/role functioning (including employment status), and the Short Form 36 question (SF 36) generic quality of life instrument.

Blood Sampling

Blood samples will be drawn for analysis as a part of this study. One 10 ml sample of peripheral blood will be obtained from each patient prior to surgery and stored. Genomic DNA for analysis will be obtained from this sample and analyzed for the presence of candidate SNPs (single nucleotide polymorphisms) including APOE. 10 ml of blood will also be sampled at baseline, end of CPB, postoperative days 1, 2 and day of the MRI scan, and at 6 weeks (\pm 2 weeks), and 1 year (\pm 1 month) follow-up for assessment of inflammatory and proteomic markers. In addition, 10ml of blood will be drawn to assess HCQ drug levels at end of CPB and day of the MRI scan. Subjects will have the option to sign the Genomic and Proteomic Database Repository (IRB#00015651) consent form, allowing the banking of any remaining plasma and DNA samples for future research. If a creatinine level is not drawn for standard of care post-operatively, one 6ml blood sample will be drawn to assess kidney function (GFR \geq 30 ml/min/1.73 sq.m) for

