gadolinium administration safety. Up to 106 ml of blood will be collected during the 12 month study participation period.

Ophthalmic Assessments

Hydroxychloroquine associated retinopathy is rare and thought to be associated with cumulative dosage and with chronic administration. Although toxicity is not expected in the short-term dosing schedule in this protocol, ophthalmic assessment will be performed on every subject consented as an additional measure of safety. Ophthalmic assessments will occur at baseline and at 6 weeks after surgery. Each assessment will take approximately 1.5 hrs and will include visual acuity, optical coherence tomography (OCT) of the macula, and multi-focal electroretinogram (ERG). Ophthalmic assessments will be performed in the undilated eye, but the eye may need to be dilated in the event of minuscule pupils. A report confirming the absence of retinal abnormalities (that are contraindications to hydroxychloroquine administration – see exclusion criteria #18) will be provided to the study team by an ophthalmologist ([name]) prior to initial dosing. The 6-week report will document serial changes and will be evaluated as part of the safety profile.

ECG for QTc evaluation

Standard of care (SOC) ECG will be used to evaluate QTc prior to HCQ dosing. For males QTc>450msec and for females>470msec will be ineligible to receiving HCQ dosing that day. If no ECG will be obtained per SOC, the research team will perform an ECG at baseline and prior to daily HCQ dosing.

Standard of Care

- Anesthesia (premedication, choice of anesthetic technique and drugs to be administered) per standard of care
- Surgical and postoperative care per standard of care
- Clinical status will be monitored throughout the duration of the procedure
- Standard of Care ECG if performed will be used for evaluation of QTc prior to HCQ dosing throughout the study.

Selection of Subjects

To be eligible for inclusion into the study, each patient will have to fulfill the following criteria:

Inclusion Criteria

1. Male or female, age \geq 50 years old.
2. Patients scheduled to undergo cardiac surgery (CABG, CABG + Valve, Valve) with CPB or general surgery (e.g. orthopedic, abdominal, urological).
3. Patient has voluntarily signed and dated the study-specific informed consent form approved by Duke University Health System Institutional Review Board (DUHS IRB)

Exclusion Criteria

1. Cardiac surgery scheduled to be performed without cardiopulmonary bypass

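### The only hydroxychloroquine level scheduled at surgery, and one inflammatory-marker sample, are timed to the end of cardiopulmonary bypass, which the noncardiac half of the cohort does not have

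*Combined protocol and SAP*

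**What the plan says.** All references are to the combined protocol and SAP.

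- **Purpose of the study.** The first primary purpose is "Obtain data on the pharmacokinetics of hydroxychloroquine during surgery" and the third is "Determine the effect of hydroxychloroquine upon perioperative inflammation". Neither is restricted to cardiac patients. The same section expects the wider cohort to let outcome differences between surgery types be examined.
- **Blood Sampling, drug levels.** "In addition, 10ml of blood will be drawn to assess HCQ drug levels at end of CPB and day of the MRI scan".
- **Blood Sampling, inflammatory and proteomic markers.** "10 ml of blood will also be sampled at baseline, end of CPB, postoperative days 1, 2 and day of the MRI scan", and again at 6 weeks and 1 year.
- **Hydroxychloroquine Administration.** There are five phases, each with three cardiac and three noncardiac evaluable subjects. In Phases 1 to 4 the first dose precedes surgery; Phase 2, for example, reads "1000 mg HCQ on the day prior to surgery followed by 400 mg daily until the day of MRI imaging on postoperative day 1-5". In Phase 5 the first dose is "1000 mg HCQ 1-2 hours after separation from CPB or at end of noncardiac surgery".
- **Selection of Subjects.** Inclusion criterion 2 admits cardiac surgery using CPB, or general surgery. Exclusion criterion 1 removes cardiac surgery planned without CPB. The cardiac/noncardiac split is therefore also the split between planned CPB and none.
- **Cohort and blood volume.** Up to 50 patients "will be prospectively enrolled over a 1-year period to provide 30 evaluable subjects". The volume statement is "Up to 106 ml of blood will be collected during the 12 month study participation period".

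**The concern.** The MRI takes place on postoperative day 1 to 5, so the end-of-CPB draw is the only HCQ level taken at the time of surgery. A noncardiac subject never reaches that time point, and the sampling text offers no substitute. The dosing text shows that the need was recognised elsewhere: for Phase 5 it pairs separation from CPB with the end of noncardiac surgery. The sampling text does not carry that pairing over.

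If staff follow the schedule literally, half of the subjects dosed before surgery contribute nothing at surgery to the first listed purpose. Half of the evaluable cohort also lacks the marker sample closest to the surgical insult. Samples not drawn in the operating room cannot be recovered later. The loss falls entirely on one surgery type, which works against the stated interest in differences by surgery type.

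**Working it through.** This is a count, not a power calculation. The documents give no effect size or variance for HCQ levels, and none is needed.

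**1. Reproduce the plan's own totals.**
- Evaluable subjects: 5 phases × (3 cardiac + 3 noncardiac) = 15 + 15 = 30. This matches the stated 30.
- Maximum blood volume: 10 ml (DNA) + 7 × 10 ml (markers: baseline, end of CPB, days 1 and 2, MRI day, 6 weeks, 1 year) + 2 × 10 ml (HCQ levels) + 6 ml (creatinine, if not drawn in routine care) = 106 ml. This matches the stated 106 ml, and it includes both CPB-timed draws.

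**2. HCQ levels at surgery after dosing, as scheduled.**

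| Phases | Cardiac | Noncardiac | Total |
|---|---|---|---|
| 1 to 4 (dosed before surgery) | at most 12 of 12 | 0 of 12 | at most 12 of 24 (50%) |
| 5 (first dose after CPB or at end of surgery) | 0 of 3 (sample precedes dose) | 0 of 3 (no CPB) | 0 of 6 |
| All | at most 12 of 15 | 0 of 15 | at most 12 of 30 (40%) |

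Phases 1 to 4 supply 4 × 3 = 12 subjects per stratum. In Phase 5 cardiac subjects the dose follows separation from CPB by 1 to 2 hours, so an end-of-CPB level is a pre-dose value.

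**3. Marker sample at the close of the procedure, as scheduled.** At most 5 × 3 = 15 of 30, with 0 of 15 noncardiac.

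**4. What noncardiac subjects keep.** They keep the MRI-day HCQ level and up to six of the seven marker samples. Six is a maximum, because an MRI on day 1 or 2 coincides with another marker time. The MRI-day level does not stand in for exposure at surgery. In Phase 1 it falls 2 to 6 days after the single dose (day −1 to day 1, or to day 5). In Phases 2 to 4 further dosing is scheduled after the first dose.

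**5. Volume with and without the missing draws.**
- Noncardiac as written: 10 + 6 × 10 + 1 × 10 + 6 = 86 ml.
- Noncardiac with both samples added: 86 + 10 + 10 = 106 ml, equal to the stated ceiling.

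**6. Counts with a noncardiac time point.** Levels at surgery after dosing in Phases 1 to 4 rise to at most 24 of 24. Marker samples at the close of the procedure rise to at most 30 of 30.

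**The case against.** The strongest reply is that this is an omission rather than a contradiction. No two sections conflict, the dosing text already pairs CPB with the end of noncardiac surgery, and a sensible coordinator might apply the same pairing to blood draws. The single 106 ml ceiling is not split by surgery type and, being a maximum, supports neither reading. That much stands: nothing forbids a noncardiac draw. A reader might infer that noncardiac subjects cannot have a level at surgery, or that leaving them out was intended. The text supports neither, only that none is scheduled for them.

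The reply can also say that little depends on the sample. The primary endpoint is the 6-week change in cognitive score, the escalation review does not list HCQ levels among its measures, and the analysis section specifies no analysis of HCQ levels. It would therefore be wrong to infer that the cognitive endpoint or the dose-escalation decisions are compromised. Nor are noncardiac subjects without any HCQ level, since the MRI-day sample remains.

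A reader might further infer that a planned comparison of HCQ levels by surgery type is lost. The Purpose section speaks of outcome differences by surgery type but does not say whether HCQ levels are among those outcomes. The documents settle this neither way.

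Finally, one level per subject is not pharmacokinetics during surgery even for cardiac subjects. That is correct, and it limits what the repair can achieve. It does not justify having no scheduled level in half of the cohort, when this is the first purpose the pilot lists and the remedy is one phrase.

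**Conclusion.** The point holds as a gap in the sampling schedule and should be fixed. Followed as written, the plan schedules a level at surgery after dosing for at most 12 of 24 evaluable subjects in Phases 1 to 4, and for none of the 12 noncardiac. It schedules a marker sample at the close of the procedure for at most 15 of 30, and for none of the 15 noncardiac. This weakens purpose 1 directly. It weakens purpose 3 and the interest in surgery type to a lesser degree, because the other marker times remain.

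The counts assume that staff follow the schedule literally, that each phase fills at three and three, and that only evaluable subjects are counted. Replaced subjects could add cardiac levels but, under the literal text, no noncardiac ones. If sites in practice drew noncardiac samples at the end of surgery, the loss would be smaller; the documents do not say that they would.

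**What to change.** In Blood Sampling, change the time point for both the HCQ level and the inflammatory/proteomic sample to *end of CPB (cardiac) or end of surgery (noncardiac)*. Record the clock times of the last HCQ dose and of the sample, because the end of CPB and the end of surgery are different procedural times and the interval since dosing will vary. For Phase 5, state whether the noncardiac sample is drawn before or after the dose, since both would otherwise fall at the end of surgery with no order defined. None of this changes a dose or a dosing time.

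The cost is a short amendment, two recorded times per sample, and up to 15 marker + 15 HCQ = 30 further draws of 10 ml, with their assays, among evaluable subjects. There would be more if replaced subjects are also sampled. The noncardiac maximum rises from 86 to 106 ml, so the blood-volume statements can stay as they are. The resulting levels should be reported as exposure at a single time point, not as a full pharmacokinetic description.

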MR Image review for presence of BBB disruption

A board-certified neuroradiologist, blinded to the clinical and surgical variables, will read the MRI, and also review the precontrast and postcontrast FLAIR images for the presence of HARM (hyperintense acute reperfusion marker) and classify it by location (sulcal, ventricular, and/or

generalized) and severity (mild, moderate, or severe), according to the classification scheme described by Merino et al.(9)

Quantitative DCE MRI of BBB disruption

Using T1 time series data, we will calculate the rate at which the contrast agent passes from the vascular compartment into the tissue compartment, K_i , using the Patlak formulation of tracer leakage.(33) Plasma levels of gadolinium will be sampled from a region-of-interest in the sagittal sinus. Parenchymal region-of-interest measurements will be made in the white matter.

Privacy, Data storage & Confidentiality

Primary study data will be images acquired from the neuroimaging procedures and patient case report forms. Preprocessing software will strip any MR image headers that may contain subjects' names, as well as de-skull the images to prevent any visual reconstruction of subject identity, and will rewrite the resulting data as image volumes identified by subject identification number only. The post-processed imaging data will be stored electronically on a secure computer housed at the Center for Advanced Magnetic Resonance Development, as well as archived on DVD storage medium to be placed into a locked cabinet. The data collected in the Case Report Forms will be obtained specifically for research and internal quality assurance purposes. While the hemodynamic, laboratory, and historical data will be collected at the time of the intraoperative study, the information is all part of the routine medical record documenting the patient's care in the perioperative period. The patient's identity will be specifically protected and confidentiality will be maintained by reporting any published material by patient number. All genetic data will remain confidential and will not be available to the patient, the patient's family or physician. All genetic material for patients enrolled into this study will be identified only through unique study identification number. This unique study number will also be linked to a barcode affixed to each study sample, collected according to protocol. For future review or database dissemination, the study number and the barcode will be the only identifying information associated with the subject. The subject's name, social security number, or any other "identifying information" will not be linked to the individual subject. At the time of consent, the patient will be asked to sign an authorization of release to provide us permission to obtain medical information in the event the patient returns to the hospital, health care facility, or family doctor for indications of chest pain, congestive heart failure, heart attack, or stroke during the course of the study. At the one year follow-up visit, the patient will be asked to complete a medical condition questionnaire. This information will be used to determine any changes in health since surgery. Participants will not be identified by name in any analysis of these data, nor any presentation or publication resulting from the analysis of these data.

